*** Brief Description (using layman's terms) - 500 words or less:**

Frail Veterans are at increased risk for poor surgical outcomes, and as the Veteran population grows older and more frail, there is a critical need to identify effective strategies for reducing surgical risks for these patients. Prior research shows that inter-disciplinary rehabilitation strategies deployed after surgery enhance recovery and improve outcomes by building strength and improving nutrition. We believe that similar improvements may be obtained by using similar interventions before surgery to "prehabilitate" patients' capacity to tolerate the stress of surgery. The proposed research will examine the feasibility of a new, prehabilitation intervention aimed at improving postoperative surgical outcomes through preoperative exercise training and nutritional supplementation. Findings from the study will inform the design of a larger randomized controlled trial of the prehabilitation intervention. If proven effective, prehabilitation could benefit as many as 42,000 frail Veterans who are scheduled for major elective surgery each year.

*** Abstract. Please provide a brief description of the study.**

Background: Frail Veterans are at increased risk for poor surgical outcomes. Although surgeons operate safely on even the oldest old, if the elder is also frail, the stress of surgery can result in significant mortality, morbidity, and institutionalization. Frailty is a clinical syndrome marked by muscle atrophy, diminished strength, decreased physical activity, and exhaustion. It is independent of any specific disease, but it increases with age, and is a more powerful predictor of increased perioperative mortality, morbidity, length of stay, and cost than predictions based on age or comorbidity alone. As the Veteran and US populations grow older and more frail, it is critically important to identify effective strategies for improving the surgical outcomes of these patients.

"Prehabilitation" has the potential to improve surgical outcomes among the frail. Prior research demonstrates that inter-disciplinary rehabilitation strategies deployed after surgery enhance recovery and improve outcomes by building strength, improving nutrition, and optimizing home supports. Based on this success, there is growing interest in deploying similar interventions before surgery in what some call "prehabilitation." By modifying physiological and environmental risks, prehabilitation aims to augment patients' capacity to compensate for the stress of both surgery and recovery. Frail patients will likely benefit disproportionately from prehabilitation because they have the most diminished capacity to adapt to the stress of surgery. However, prehabilitation has not yet been studied in either Veteran or specifically frail populations.

Objectives: We will examine the feasibility of a novel, multifaceted pre-habilitation intervention aimed at improving postoperative outcomes for frail Veterans undergoing major abdominal surgery. Specific aims are to:

- (1) Estimate rates of recruitment, randomization, retention, and compliance with the prehabilitation intervention;
- (2) Measure (a) physical performance, (b) pulmonary function, and (c) nutrition at baseline and 2-week intervals to estimate changes over time and explore the optimal duration of prehabilitation (2 vs. 4 vs. 6 weeks); and
- (3) Estimate overall and treatment-specific summary statistics for postoperative outcomes in terms of 30- and 90-day (a) mortality, (b) major complications, (c) length of hospital stay, (d) health-related quality of life, (e) quality of surgical care, and (f) change in level of independent living.

Methods: This randomized pilot study will enroll a consecutive cohort of up to 50 Veterans identified as frail using a standardized frailty assessment and scheduled for major abdominal surgery on the general or urological surgery services at the VA Pittsburgh Healthcare System. We will randomize participants 1:1 to receive either: (1) standard preoperative optimization by the Interdisciplinary Medical Preoperative Assessment Consultation & Treatment Clinic (IMPACT), or (2) prehabilitation + standard IMPACT optimization. The 6-week long prehabilitation intervention

will include (1) strength and balance training; (2) inspiratory muscle training; and (3) nutritional coaching and supplementation. Assessments will include standard postoperative outcomes as well as the Short Physical Performance Battery to measure physical performance, Maximal Inspiratory Pressure to measure pulmonary function, and both prealbumin and the 7-point Subjective Global Assessment to measure nutrition. Outcomes will be assessed 30 or 90 days after surgery. Compliance with the prehabilitation regimen will be assessed through patient logs and pedometers. Analyses will inform the development of a larger randomized controlled trial testing the prehabilitation intervention. Findings will be relevant for the as many as 42,000 frail Veterans scheduled for major elective surgery each year.

*** Describe the study objectives. Please include primary aim and hypothesis, if applicable any secondary aims and hypotheses.**

We will examine the feasibility of a novel, multifaceted pre-habilitation intervention aimed at improving postoperative outcomes for frail Veterans undergoing major abdominal surgery. Specific aims are to:

- (1) Estimate rates of recruitment, randomization, retention, and compliance with the prehabilitation intervention;
- (2) Measure (a) physical performance, (b) pulmonary function, and (c) nutrition at baseline and 2-week intervals to estimate changes over time and explore the optimal duration of prehabilitation (2 vs. 4 vs. 6 weeks); and
- (3) Estimate overall and treatment-specific summary statistics for postoperative outcomes in terms of 30- and 90-day (a) mortality, (b) major complications, (c) length of hospital stay, (d) health-related quality of life, (e) quality of surgical care, and (f) change in level of independent living.

*** Provide a summary of the background of the study and explain how this research will contribute to existing knowledge. Describe previous studies that provides a basis to show that the proposed research can be carried out without undue risk to human subjects.**

A.1. What is frailty? Although frailty can be defined in many ways, an international panel of experts convened in 2011 agreed that it is a multidimensional construct consisting of 6 domains (physical performance, gait speed, mobility, nutritional status, mental health and cognition) that together indicate increased risk of death, disability and institutionalization.³⁰ Frailty goes beyond organ-specific comorbidities to characterize a broader state of global health that extends to both physical and cognitive attributes.³¹⁻³⁴ Frailty increases with age, but the elderly are not necessarily frail, and the young are not necessarily robust. As such, *frailty can be conceptualized as a measure of "physiologic reserve,"* defined as the critical threshold at which external stressors overwhelm the human body's multiple mechanisms for adaptation, resulting in decompensation (i.e., acute illness or injury).¹ Frailty is the consequence of a process whereby small deficits accumulate in multiple adaptive systems, any one of which might be clinically insignificant, but together they produce significant vulnerability to stress that can lead to catastrophic decompensation. Thus, a robust 80 year old might survive an operation that a frail 60 year old might not.

A.2. Frailty will increase as the US and Veteran populations age, constituting a growing vulnerable population. By 2040, the population over age 65 is expected to double and continue expanding thereafter.³⁵ Many aging Veterans will develop decreased physical and cognitive capacities,³⁶⁻³⁸ making them vulnerable to impaired decision making,³⁹ loss of independence,⁴⁰ polypharmacy⁴¹ and elder abuse.⁴² The VA's Strategic Plan for 2014-2020 recognizes that "geriatric care will continue to be a significant portion of VA's health care,"⁴³ and the VA Office of Geriatrics and Extended Care includes treatment of the frail in its mandate.⁴⁴

A.3. Frail Veterans frequently undergo major surgery with dramatically increased morbidity and mortality. Some form of frailty is present in half of all Veterans undergoing colorectal and cardiac surgery,⁵ and one third of the US population is expected to undergo a major surgical procedure within the last year of life.⁴⁵ Some frail patients clearly benefit from surgery through improved symptom management and extended life. However, the high rate of surgical morbidity and mortality among the frail suggests that for many, surgery confers significant burdens for patients, families, and society at large.⁴⁻⁹ For example, compared to robust patients, frail surgical patients are less likely to be discharged to home,⁸ more likely to be readmitted within 30 days,^{5,9} and have substantially increased rates of perioperative mortality and complications.^{4,6,7,9} In fact, our preliminary analysis demonstrates similar patterns across 1,632 major abdominal operations performed at VAPHS from 2010 to 2014 where 192 (11.8%) Veterans with differing degrees of frailty suffered dramatically increased mortality, morbidity and length of stay. Even in the mildly frail, 30-day postoperative mortality was 10 times greater than among the robust (4% vs. 0.4%, $p < .001$), and increased dramatically with increasing frailty. However, little is known about how to improve the surgical outcomes of frail patients.

A.4. A recent expert panel of VA surgeons identified several potential targets for improving surgical care of Veterans before, during, and after surgery.⁴⁶ Targets included improved preoperative decision-making, optimized intraoperative anesthetic management, and postoperative prevention of frailty-associated complications like delirium. For example, the panel hypothesized that if patients and surgeons were accurately informed of frailty-associated risks, many would choose less invasive procedures or even non-surgical therapies, thereby avoiding predictable complications. In fact, our previous work provides preliminary support for this hypothesis: In one of the only prospective attempts to improve the surgical care of the frail, we demonstrated that pre-operative, palliative care consultation ordered by a surgeon to inform and clarify surgical decision-making was associated with a markedly reduced odds of dying, even after controlling for age, frailty, and whether or not Veterans had surgery (OR=0.27; 95% CI 0.11-0.68, $p=.006$).⁴⁷ Some of these Veterans opted out of surgery, but most proceeded to the operating room, thus demonstrating the critically important need to identify effective strategies for mitigating frailty-associated risks of those choosing surgery.

A.5. Prehabilitation is a promising, yet largely untested, strategy for mitigating surgical risk. The concept of prehabilitation *before* surgery is rooted in the demonstrated success of cardiac rehabilitation to advance activity, modify cardiac risk factors, and foster healthful lifestyles *after* surgery through a standardized, structured, exercise-educational-behavioral strategy.¹⁰ The orientation of cardiac rehabilitation to surgical recovery evolved from its original function to first mobilize and then advance activity for patients who had survived what was usually a devastating myocardial infarction and/or who had undergone what was usually a severely debilitating coronary artery bypass procedure.⁴⁸ As demonstrated by several systematic reviews, similar strategies have proven successful not only for cardiac surgery,¹⁰ but also for orthopedic,^{11,13} lung,^{14,49} and abdominal surgery.¹² However, rather than waiting until after the surgery to initiate these proven strategies, there is growing interest in deploying similar exercise-educational-behavioral strategies *before* surgery to mitigate perioperative risks by increasing patients' capacity to respond to intraoperative stress and accelerate postoperative recovery.^{12,19,50} Several cohort and small randomized controlled trials (RCTs) have explored the feasibility and impact of prehabilitation for cardiac, orthopedic, and major abdominal operations.^{16-18,20,21} However, these studies focused on relatively high-functioning patients, and thus both the feasibility and effectiveness of prehabilitation among specifically frail populations remains uncertain.

A.6. Prehabilitation is most promising among the frail. Although prehabilitation may benefit everyone, frail patients likely have the most to gain because they have the greatest deficits in physiologic reserve, and thus even modest improvements in strength, balance, and nutrition may prevent the physiologic decompensation that leads to poor outcomes.^{51,52} However, it remains unclear if frail patients can fully comply with intensive physical therapy (PT), and even if they do, it is not clear if they will build strength, muscle mass, aerobic capacity, and nutrition demonstrated in more robust populations.⁵³ A recent review demonstrates preliminary feasibility, safety and effectiveness of PT programs focused on frail populations,⁵⁴ but because the most effective interventions lasted ≥ 5 months, it remains uncertain if clinically significant benefits can be achieved in the 4-6 weeks that typically elapse between diagnosis and surgery. To begin examining these questions, researchers in Canada are conducting a multi-site RCT of prehabilitation for *cardiac* surgery.⁵⁵ *However, further research is needed to demonstrate the feasibility and effectiveness of frailty-focused prehabilitation in the non-cardiac surgery that accounts for the majority of surgery conducted in US Veteran populations.*

A.7. We therefore developed a multifaceted prehabilitation intervention for frail patients scheduled for major abdominal surgery. We will leverage the existing standard of care at VAPHS through which all patients scheduled for surgery are routinely evaluated for frailty as part of a standard preoperative risk assessment (but not risk mitigation). For those identified as frail, we will offer prehabilitation focused on increasing physiological reserve through (a) strength and balance training to support the improved outcomes associated with early mobilization after abdominal surgery,⁵⁶ (b) inspiratory muscle training to reduce postoperative pulmonary complications⁵⁷ and (c) nutritional coaching and supplementation to enhance physical performance⁵⁸ and wound healing.⁵⁹ We will also arrange occupational and physical therapy consults to identify and supply needed durable medical equipment.

A.8. Conceptual model for prehabilitation. Our approach to prehabilitation is informed by a conceptual model adapted from Hoogeboom and colleagues¹² to illustrate how prehabilitation might improve postoperative outcomes by increasing physiological reserve at the time of surgery. As indicated by the solid lines, the decreased physiological reserves of frailty limit capacity to adapt to the stress of surgery, leading to worse outcomes. Prehabilitation aims to increase physiological reserve at the time of surgery by increasing physical and pulmonary function along with improved nutrition, thereby increasing adaptive capacity and improving outcomes including decreased mortality, complications length of stay and improved quality of life.

PRELIMINARY STUDIES

B.1. Our interdisciplinary research team has the expertise to accomplish this study. [name] is a general surgeon and former recipient of an HSR&D Career Development Award focused on improving the process of surgical informed consent. In 2014, he began collaborating with [name] (Co-I) to validate the Risk Analysis Index (RAI) of frailty used in this study (B.2). He is a consultant on several quality improvement (QI) projects related to surgical frailty at the Omaha, Atlanta, Nashville and Pittsburgh VAMCs and the University of Pittsburgh. [name] is a geriatrician and cardiologist who directs the VAPHS Cardiac Rehabilitation Center. He has extensive experience with exercise physiology trials (B.3), including an ongoing RR&D I01 (F0834-R) aimed at understanding the effects of different types of exercise training on the functional capacity of heart failure patients. [name] is a vascular surgeon and health system administrator with geriatric training who implemented the Frailty Screening Initiative at the Omaha VAMC (B.4), collaborated with [name] to validate the RAI, and serves as a consultant with similar initiatives at several VA and non-VA centers. [name], the Chief of Surgery at VAPHS, has expertise in surgical QI. With [name], he implemented procedures at VAPHS to systematically

screen all preoperative patients for frailty, and will work closely with the team to implement the prehabilitation procedures proposed here. [name] brings key expertise as a leader in the field of inspiratory muscle training (IMT),⁶⁰⁻⁶⁵ having developed a convenient and effect regimen for IMT (B.5). He is collaborating on [name] RR&D I01 (B.3), and he will guide the IMT component of the present study.

B.2. Development, validation, and implementation of the Risk Analysis Index (RAI) of frailty. None of the existing tools for measuring frailty have proved suitable for widespread, prospective clinical screening. To fill this gap, Drs. [name] and [name] developed, validated and refined the RAI that can be calculated retrospectively from VA Surgical Quality Improvement Program (VASQIP) data or prospectively from a 2-minute 14-item survey. Both versions of the RAI yield a continuous score that captures a full range of frailty from robust (0-15) to mild (16-25), moderate (26-35) and severe frailty (≥ 36). From July 2011 to September 2015, they used the 14-item survey to assess frailty in a consecutive cohort of 6,905 patients scheduled for surgery at the Omaha VAMC. In this cohort, the RAI has strong predictive power for 6-month mortality (c-statistic=0.772).⁶⁶ At a cutoff of ≥ 16 , the RAI survey classified 12.5% of the cohort as frail with a sensitivity of 0.50 and specificity of 0.90. By linking this cohort to VASQIP data, they compared the RAI to the previously validated, retrospectively calculated modified Frailty Index (mFI)⁶⁷ in a sub-sample of 1,024 patients where the RAI survey (c=.797) performed on par with the mFI (c=.811), thus establishing preliminary convergent validity with the advantage of prospective assessment that can inform real-time clinical decisions. Based on these data, the RAI questionnaire was implemented as standard of care for pre-surgical risk stratification at the Omaha, Pittsburgh, Atlanta, Nashville and Phoenix VAMCs.

B.3. Effective implementation of exercise training programs in frail heart failure patients and recruiting subjects into training trials. [name] was Site PI for both the NHLBI aerobic training trial HF-ACTION⁶⁸ and the NCCAM Tai Chi Mind-Body Movement Therapy for Patients with Chronic Heart Failure.⁶⁹ He is skilled in the prehabilitation techniques planned for this investigation, reliably achieving both training effects and endpoints. For example, in a trial of older female patients, those randomized to a strength training program similar to that proposed here had significantly increased strength ($43.4 \pm 8.8\%$ vs. $-1.7 \pm 2.8\%$ in controls, $p= 0.001$) and endurance ($299 \pm 66\%$ vs. $1 \pm 3\%$, $p= 0.001$).⁷⁰ [name] RR&D I01 is currently randomizing 200 heart failure patients to regimens similar to those proposed here that focus on strength training and IMT.

B.4. The Omaha Frailty Screening Initiative (FSI) is the first feasible and effective facility-level intervention to improve postoperative survival among frail Veterans. While Chief of Surgery at the Omaha VA, [name] began using the RAI to screen pre-surgical patients for frailty. Those identified as frail were subjected to an administrative review aimed at clarifying surgical decision-making through informal discussions with surgeons, anesthesiologists and palliative care physicians focused on each patient's frailty and frailty-associated risk.^{47,71-73} By comparing outcomes after FSI implementation to historical controls, he and [name] found that 180-day survival among frail patients improved 7-fold after implementing the FSI (OR 7.50, 95% CI 4.08-13.79), reflecting a drop in 180-day mortality from 23.9% to 4.5% ($p<.001$).⁷⁴

B.5. IMT improves pulmonary function in as little as 2 weeks. [name] study of IMT in advanced heart failure patients found that dyspnea symptoms improved when maximal inspiratory pressure increased 24% (51 ± 21 to 63 ± 23 cm H₂O, $p=.0001$) only 2 weeks after initiating an IMT regimen that was far more convenient and efficient than others which had been studied at that time.⁶² A subsequent study also in heart failure patients showed that IMT significantly improved

gait speed and quality of life.⁶³ This experience informs both the methods presented here, as well those of [name] RR&D I01.

*** Describe the overall significance of the research in terms of the problem to be studied and potential findings, as well as its relevance to the care of veterans, the VAPHS, and the VHA:**

C.1. The proposed research has potentially high impact because it addresses the needs of as many as 42,000 frail Veterans scheduled for major elective surgery each year.²⁹ These patients experience disproportionately poor outcomes and accrue markedly higher costs, thus representing a highly significant opportunity to improve the processes of surgical care through prehabilitation strategies to yield a practical, preventative strategy for improving both quality and quantity of life for vulnerable, frail Veterans.

C.2. Prehabilitation for the frail is innovative because it shifts established rehabilitation strategies to the preoperative period and focuses those strategies on the frail Veterans most likely to benefit. As such, it addresses a critical gap in the science of frailty research, and does so with a focused strategy to direct preventative resources to the limited population at greatest risk and thus most likely to benefit.

C.3. The proposed research is directly aligned with VA's operational imperatives. Our study "advances healthcare innovation" (Theme 3 of the VA's Strategic Plan⁷⁵) by developing an innovative, preventative healthcare intervention that "anticipates and meets the unique needs of... [the] most vulnerable Veterans" (Blueprint Strategy 1). It also aligns with HSR&D Priority Areas A (access for vulnerable Veteran populations) and B (health equity) along with the Office of Geriatrics and Extended Care Service's focus on "optimizing the health and well-being of Veterans with multiple chronic conditions, life-limiting illness...and frailty."⁴⁴ Letters of support demonstrate that Assistant Deputy Under Secretary of Health for Clinical Operations and Management, [name], as well as the Director of Geriatrics and Extended Care Operations, [name], are enthusiastic partners in the proposed research and are prepared to use study findings to guide future, system-wide initiatives to improve the quality of patient-centered surgical care throughout VHA. There is also significant interest from CMS Deputy Chief Medical Officer, [name], indicating that the VA can again lead the nation in developing high-value medical care.

Research study methods

Research Study Methods

Describe all study related procedures following enrollment of a subject in this study.

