*** Research Procedures/Interventions:**

D.1. Overview. We will conduct a randomized pilot study of a prehabilitation intervention in a consecutive sample of up to 50 frail patients scheduled for elective major abdominal surgery at the VAPHS. Participants will be recruited from the mandatory preoperative IMPACT clinic where all patients are routinely screened for frailty. Frail patients agreeing to participate will be randomized 1:1 to (a) standard preoperative optimization by the IMPACT clinic or (b) prehabilitation + standard IMPACT optimization. The prehabilitation intervention will deploy existing cardiac rehabilitation resources to provide (a) strength and balance training, (b) respiratory muscle training, and (c) nutritional coaching and supplementation. Using physical performance tests, biomarkers, chart review, survey instruments, and patient logs, we will assess the feasibility of the recruitment, randomization, retention and assessment procedures, compensating patients for their time.

D.4. Eligibility criteria. We will include all patients with RAI>16 scheduled for major abdominal surgery on the general or urological surgery services. Major surgery is defined according to VASQIP criteria to include cases requiring general, epidural, or spinal anesthesia.

For general and urological surgery, it includes 270 standard, 356 intermediate, and 34 complex procedures, but excludes 291 low risk, "minor" surgical procedures with limited morbidity (e.g., abscess drainage, lipomas, or hemorrhoids). From these major surgeries, we will include those abdominal procedures that deliberately violate the peritoneal or retroperitoneal spaces. For example, from the general surgery service we will include all bowel resections, biliary procedures, and abdominal wall reconstructions, but exclude open, anterior inguinal hernia repair. The list of included CPT codes (see Appendix) represents 56% and 35% of the general and urological surgery volume at VAPHS, respectively (Table 2 below). Given the burden of comorbidity among the frail, we anticipate that many eligible Veterans will have concurrent cognitive impairment or dependent living situations. These limitations need not preclude inclusion so long as the patient can provide first-person informed consent and participate in the prehabilitation regimen described below (D.6). No other exclusions are planned.

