person-time where person-time is defined as the amount of time a patient is followed from study start to either the end of study, death or loss to follow-up (whichever occurs first). We will also compute summary statistics (mean, median, standard deviation, range) for length of hospital stay, health-related quality of life, quality of surgical care and recovery to independent living. We will make assessments overall and by treatment group. While our emphasis is to assess feasibility, we will also attempt to assess if differences exist between the intervention and control conditions with regards to these post-operative measures.

D.11. Justification of Pilot sample size. Based on the historical surgical volume at VAPHS, the participating surgical services will treat 54 eligible patients who meet our inclusion criteria during a 7 month recruitment window (Table 3). We are not estimating the effect size between intervention and control conditions. Although there is a tradition of using pilot studies to do so, there is growing consensus that this approach is ill-founded because the small samples result in imprecision that makes power estimates unreliable.²³ Therefore, based on recruitment and retention rates estimated here (Aim 1), we will power our subsequent study based on “minimum clinically meaningful differences” defined for each outcome *a priori*.²⁴

Table 3: Sample Size Estimates	General	Urology	Total
Total Surgical Cases/year	1488	610	2098
VASQIP Eligible Cases/year	748	298	1046
Proportion Abdominal	56.2%	35.3%	$\bar{x}=50.2\%$
Proportion Frail	12.0%	10.3%	$\bar{x}=11.5\%$
Eligible Cases/year	70.9	21.5	92.4
Eligible Cases/7 month recruitment	41.4	12.5	53.9

References:

* Please provide a list of references (Multi-site protocols: You may reference the page numbers in the original protocol):

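### The 54 eligible patients expected in 7 months (D.11) are not supported by Table 3's own rows, which give about 36, or by the A.3 count, which gives about 22 to 37 if it is the full series

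*Combined protocol and SAP*

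**What the plan says.** D.11 rests the pilot's size on the expected pool. "Based on the historical surgical volume at VAPHS", it says, "the participating surgical services will treat 54 eligible patients who meet our inclusion criteria during a 7 month recruitment window". Table 3 builds this up by service, with rows that include "VASQIP Eligible Cases/year 748 298 1046" and "Proportion Abdominal 56.2% 35.3"% (general, then urology), and frail shares of 12.0% and 10.3%. It ends at 70.9 + 21.5 = 92.4 eligible cases a year and 53.9 per 7 months. D.11 offers no effect-size or precision argument; it says expressly that no between-arm effect size is being estimated.

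D.1 plans a "consecutive sample of up to 50 frail patients scheduled for elective major abdominal surgery at the VAPHS".

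A.3 gives a separate historical count from the same site. It reports a preliminary analysis "across 1,632 major abdominal operations performed at VAPHS from 2010 to 2014 where 192 (11.8%) Veterans with differing degrees of frailty" had worse outcomes. It does not state the start and end months, the surgical services covered, or whether the series is complete. Neither section refers to the other.

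**The concern.** A.3 and D.11 describe the same hospital, the same broad class of surgery and nearly the same frail share (11.8% in A.3, a mean of 11.5% in Table 3), yet they imply very different numbers of frail patients a year. Table 3's stated yearly total also does not follow from the rows above it.

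What is at stake is the planned size, precision and duration of a feasibility pilot. Aim 1 is to estimate recruitment, randomization, retention and compliance rates with confidence intervals. If the true pool is near 36, or lower, then 50 patients cannot be enrolled in 7 months even if everyone agrees. The intervals would be wider than a reader of D.11 would expect, or recruitment would take longer.

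**Working it through.** **Table 3, last step.** 92.4 × 7/12 = 53.9. This reproduces.

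**Table 3, yearly total.** Eligible = VASQIP-eligible cases × proportion abdominal × proportion frail.

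- General: 748 × 0.562 × 0.120 = 50.4 (stated 70.9; ratio 1.41)
- Urology: 298 × 0.353 × 0.103 = 10.8 (stated 21.5; ratio 1.98)
- Total: 61.3 a year (stated 92.4)
- In 7 months: 61.3 × 7/12 = 35.7 (stated 53.9)

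The two ratios differ, so no single missing factor explains the discrepancy. Other routes do not recover 92.4 either:

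- Pooled means: 1046 × 0.502 × 0.115 = 60.4 a year.
- Total cases as the base: 1488 × 0.562 × 0.120 + 610 × 0.353 × 0.103 = 122.5 a year.
- Abdominal factor left out: 748 × 0.120 = 89.8 and 298 × 0.103 = 30.7 a year.

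The stated means are what weighting by 748 and 298 gives (50.2% and 11.5%), which fits the VASQIP row as the base.

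**A.3 count.** 192/1632 = 11.8%, as stated. The length of the period is an assumption: 5 years if both end years are whole, 4 if end to end, 3 as the shortest reading. Eligible in 7 months = 192 / years × 7/12.

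| Reading | Operations a year | Frail a year | Frail in 7 months | Share of 53.9 | Months to reach 50 at full consent |
|---|---|---|---|---|---|
| 5 years | 326 | 38.4 | 22.4 | 42% | 15.6 |
| 4 years | 408 | 48.0 | 28.0 | 52% | 12.5 |
| 3 years | 544 | 64.0 | 37.3 | 69% | 9.4 |

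At the Table 3 rows' rate, 50 patients take 50/61.3 × 12 = 9.8 months at full consent. For A.3 to yield 92.4 a year, all 192 would have to arise in 192/92.4 = 2.1 years.

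**Where the gap comes from.** Table 3's rows give 748 × 0.562 + 298 × 0.353 = 526 abdominal cases a year, and 61.3/526 = 11.7% frail, in line with A.3's 11.8%. The product error is 92.4 − 61.3 = 31.1 a year.

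| Reading | Gap, D.11 minus A.3 | Due to Table 3 product | Left over |
|---|---|---|---|
| 5 years | 54.0 | 31.1 (58%) | 22.9 |
| 4 years | 44.4 | 31.1 (70%) | 13.3 |
| 3 years | 28.4 | 31.1 (all of it) | −2.7 |

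The remainder is a matter of abdominal volume: 326 to 544 a year in A.3 against 526 from Table 3's rows.

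**Precision.** The 95% half-width for a proportion of 50% (normal approximation) is 1.96 × √(0.25/n). It is ±14 points at n = 50, ±16 at 36 or 37, ±19 at 28 and ±21 at 22. These values of n assume full consent.

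**The case against.** The strongest reply is that A.3 is not shown to be a census of the target population. It is called a preliminary analysis, looks at outcomes by frailty, and counts operations performed, whereas the trial recruits patients scheduled for surgery against a list of procedure codes. It may be a partial series. If the period is about 3 years, A.3 (64 a year) and the corrected Table 3 (61.3 a year) nearly agree. All of this stands. A reader might infer that A.3 fixes the true pool at 22 to 28; the documents do not support that, because the dates, services and completeness are not given. Other differences could push the other way: D.1 and D.4 restrict the trial to elective cases, two services and RAI above 16, while B.2 starts frailty at 16, so if A.3 is broader the eligible number is smaller.

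A reader might also divide 92.4 by the frail share and conclude that the whole gap lies in surgical volume. Table 3's own rows give 526 abdominal cases a year, so most or all of the gap is the product.

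D.4 describes the abdominal percentages as shares of each service's volume, which could suggest the total-case row as the base. That gives 122.5 a year, not 92.4, and would count minor cases that D.4 excludes.

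Finally, a reader might infer that a shortfall would be mistaken for unwillingness, or that the next trial would inherit the wrong pool. The plan does not bear this out. D.10(c) counts eligible patients actually approached, D.5 records refusals due to randomization, and D.11 takes recruitment and retention rates forward, not the pool. The figure of 50 is also a ceiling, not a target. These points limit the harm to precision and duration; they do not rescue the 54.

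**Conclusion.** The stated pool of 54 in 7 months (92.4 a year) is not supported by the protocol's own site data. Table 3's rows give about 61 a year, or 36 in 7 months, which is 66% of the stated figure. This is the firmer of the two results, since it needs only the table's printed inputs. The A.3 count gives about 22 to 37 in 7 months, on the assumptions that it is the full series and that it spans 3 to 5 years. Each of these figures is below 50 before any refusal. The conclusion that 50 is out of reach in 7 months would fail only if A.3 is a sample and Table 3's input rows are also wrong. The documents do not settle which pool figure is right, and this point does not claim to.

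**What to change.** In D.11:

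1. Correct the Table 3 product, or correct the input rows if they are what is wrong, so that the yearly total follows from them.
2. State the dates, services and completeness of the A.3 series, and reconcile it with Table 3. A sampling fraction chosen to arrive at 92.4 would not do, because Table 3's rows do not support that number.
3. Restate the expected pool: about 36 in 7 months from Table 3's rows, or about 22 to 37 if A.3 is the full series.
4. From that pool, restate either the expected enrolment with its confidence-interval width or the recruitment period.

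This is a change to planning text and one table. The cost is a less favourable stated pool or a longer stated window.
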